11. STATISTICAL CONSIDERATIONS

11.1. ACUITY X4 Endpoints

11.1.1. ACUITY X4 Primary Safety Endpoints

Safety of the ACUITY X4 lead will be evaluated by the lead-related complication-free rate (CFR) over a six-month follow-up period. [REDACTED]. Lead-related complications are lead-related adverse events resulting in permanent loss of pacing therapy, invasive intervention, injury or death. Lead-related adverse events are further defined in Section 19.3. Lead-related complications associated with attempted ACUITY X4 Lead implants will count toward this safety endpoint.

11.1.1.1. Hypotheses

The following hypotheses will be used to evaluate the Primary Safety Endpoint [REDACTED]

H₀: The Implant through 6-month lead-related complication-free rate ≤ 87%

H_a: The Implant through 6-month lead-related complication-free rate > 87%

The following hypotheses will be used to evaluate the Primary Safety Endpoint [REDACTED]

H₀: The Implant through 6-month lead-related complication-free rate ≤ 85%

H_a: The Implant through 6-month lead-related complication-free rate > 85%

[figure not shown]
[REDACTED]

[REDACTED]

11.1.2. Sample Size

The overall sample size required for ACUITY X4 is determined by the Primary Safety Endpoint. Table 12 contains the sample size estimates [redacted] based on the outlined assumptions. The sample size estimates were obtained using the normal approximation to the binomial and verified through simulations based on Kaplan-Meier methodology; Kaplan-Meier methodology will be used for the analyses. [redacted]

11.1.3. Statistical Methods

To assess safety of the ACUITY X4 leads, the Kaplan-Meier six month (180-day) complication-free rate will be calculated. [redacted]
The analysis will be conducted when the last 6-month follow-up is completed [redacted]
[redacted] Data from all implanted or attempted [redacted] [redacted] leads will be included in the endpoint analysis.

December 17, 2013
FINAL

Boston Scientific
NAVIGATE X4 Study Protocol
90874504 Version AB
Page 49 of 101

[REDACTED]

The exact follow-up time for each ACUITY X4 lead in the 180-day post-implant period will be included in the analysis via Kaplan-Meier methodology. The leads that fail to reach 180 days of follow-up (without experiencing an endpoint event prior to their end of follow-up in the period) will be censored at the time of their end of follow-up in the period. Because non-informative censoring cannot be assumed for these leads, a tipping point analysis will be performed to determine the potential effects these censored leads could have on the results if full information on each lead was present. The tipping point analysis will assign each lead that was censored prior to 180 days as either having or not having an endpoint event. The tipping point will be determined by the point at which the endpoint results turn from passing (null hypothesis) to failing (null hypothesis rejected). An exact binomial test will be performed for the tipping point analysis.

11.1.4. ACUITY X4 Primary Effectiveness Endpoint 1

The first effectiveness endpoint for ACUITY X4 is pacing capture thresholds (PCT) in the programmed configuration. This endpoint will be evaluated at 3 months post-implant. [REDACTED] For this endpoint, responders will be defined as subjects with $PCT \leq 2.5$ V in the programmed configuration.

11.1.4.1. Hypotheses

The following hypotheses will be used to evaluate Primary Effectiveness Endpoint 1 for X4 [REDACTED]:

- H₀: 3 month responder rate $\leq 75\%$
- H_a: 3 month responder rate $> 75\%$

11.1.4.2. Sample Size

[REDACTED]

11.1.4.3. Statistical Methods

ACUITY X4 Primary Effectiveness Endpoint 1 will be analyzed [REDACTED]
 [REDACTED] Subjects eligible for this analysis includes all
 [REDACTED] subjects who are successfully implanted with an ACUITY X4 lead. Subjects with LV
 pacing threshold data in the programmed configuration collected at the 3-month follow-up visit
 will contribute data to the endpoint analysis.

[REDACTED]
 [REDACTED]
 [REDACTED]
 [REDACTED]

Subjects that do not have LV pacing threshold data in the programmed configuration collected at
 the three month follow-up visit will be considered to have missing data. A tipping point analysis
 will be used to determine the potential effects subjects with missing data could have had on the
 results. The tipping point analysis will consider a range of possible responder rates in the
 subjects with missing data. The tipping point will be determined by the point at which the
 endpoint results turn from passing (null hypothesis rejected) to failing (null hypothesis not
 rejected).

11.1.5. ACUITY X4 Primary Effectiveness Endpoint 2

The second effectiveness endpoint for ACUITY X4 is pacing capture thresholds (PCT) in in the
 proximal zone (E2, E3, or E4) for [REDACTED]. This endpoint will be evaluated at 3 months
 post-implant.

Clustering electrodes on the spiral is expected to position at least one electrode adjacent to the
 myocardium. Physician investigators will therefore be instructed to use the “best” proximal
 electrode (E2, E3 or E4) as the cathode and the RV lead coil as the anode. For this endpoint
 “best” will be defined as the electrode with the lowest PCT without PNS. The PG may be used as
 an anode depending on the clinical scenario or physician preference. For this endpoint,
 responders will be defined as patients with $PCT \leq 2.5$ V in the best proximal zone at 3 months
 post-implant.

11.1.5.1. Hypotheses

The following hypotheses will be used to evaluate Primary Effectiveness Endpoint 2 [REDACTED]
 [REDACTED]

- H₀: 3 month responder rate $\leq 75\%$
- H_a: 3 month responder rate $> 75\%$

11.1.5.2. Sample Size

[REDACTED]:

- [REDACTED]
- [REDACTED]

December 17, 2013
 FINAL

Boston Scientific
 NAVIGATE X4 Study Protocol
 90874504 Version AB
 Page 51 of 101

- [REDACTED]
- [REDACTED]

[REDACTED]

[REDACTED]

[REDACTED]

[REDACTED]

11.1.5.3. Statistical Methods

ACUITY X4 Primary Effectiveness Endpoint 2 will be analyzed when the last 3-month follow-up visit [REDACTED] is completed. All [REDACTED] subjects who are successfully implanted with an ACUITY X4 spiral lead [REDACTED] eligible for inclusion in this analysis. Subjects with a best proximal zone LV pacing threshold measurement collected at the 3-month follow-up visit will contribute data to the endpoint analysis.

[REDACTED]

[REDACTED]

[REDACTED]

Subjects that do not have a best proximal zone LV pacing threshold measurement collected at the three month follow-up visit will be considered to have missing data. A tipping point analysis will be used to determine the potential effects subjects with missing data could have had on the results. The tipping point analysis will consider a range of possible responder rates that could have been observed in the subjects with missing data. The tipping point will be determined by the point at which the endpoint results turn from passing (null hypothesis rejected) to failing (null hypothesis not rejected).

11.1.6. ACUITY X4 Secondary Effectiveness Endpoint 1

The first secondary effectiveness endpoint for ACUITY X4 is sensed amplitudes in the programmed configuration. This endpoint will be evaluated at 3 months post-implant.

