10.5.7. Baseline ACUIITY X4 Lead Measurements with PSA

Documentation of PSA measurements for ACUIITY X4 leads will be required as described below for NAVIGATE X4 Study .

The required data to be collected from the implant procedure for all ACUIITY X4 includes PCT at 0.5 ms pulse width, sensed amplitude, and pacing impedance, measured with a pacing system analyzer (PSA) to verify adequate signals. Refer to Figure 6 below for a picture of the relationship between the terminal pin and ring contacts on the ACUIITY X4 quadripolar lead.

As stated in the ACUIITY X4 Physician’s Lead manual as a warning, only use the ACUIITY X4 Connector Tool for electrical connections to PSAs or similar monitors. Do not attach alligator

December 17, 2013
FINAL

Boston Scientific
NAVIGATE X4 Study Protocol
90874504 Version AB
Page 36 of 101

clips directly to the lead terminal or damage could occur. During ██████ NAVIGATE X4, it is required to perform a minimum of 6 threshold measurements as summarized in Table 8 and Figure 7 below. First, test 4 extended bipolar or 4 unipolar configurations (per physician discretion) to determine adequate electrode-myocardium contact. Test for the presence of extracardiac or phrenic nerve stimulation (PNS) for each electrode by pacing the lead at a high voltage output, using professional medical judgment to select the output voltage. If extracardiac stimulation is detected, measure stimulation PNS threshold. The four extended bipolar, or unipolar, measurements provide a relative threshold ranking among the electrodes which is associated to the proximity of each electrode to viable myocardium. Although thresholds may change, the relative ranking will be the same for bipolar measurements. Then select 2 bipolar measurements (one pair from E1 as the cathode (E2, E3, or E4 as the anode) and the other pair from E2, E3 or E4 as the cathode) to confirm the preferred distal and proximal pacing options. Use the best extended bipolar or unipolar ring electrode (from E2, E3, E4) as a cathode to any other ring electrode as an anode. Again, test for the presence of extracardiac or phrenic nerve stimulation for each electrode. If stimulation is detected, measure a PNS threshold. Refer to Table 8, Figure 6 and Figure 7 below.

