10.5.10. ACUIY X4 Lead Measurements with PG

Lead measurements, including pacing threshold (at 0.5 ms pulse width), sensed amplitude, and pacing impedance, are required to be collected using the CRT-D at implant for all implanted ACUIY X4 Leads. Pacing and sensing evaluation using the PG must be performed and the results recorded on the Implant eCRF. Lead measurements are required unless the testing is prohibited by a subject’s condition (subject has no intrinsic rhythm). The following measurements are to be taken utilizing the PG to ensure adequate sensing and pacing function of all ACUIY X4 Leads:

- Intrinsic amplitude (mV)*
- Pacing threshold (V, at 0.5 ms pulse width), details below in Table 9 and Figure 8
- Pacing lead impedance (Ω)*

December 17, 2013
FINAL

Boston Scientific
NAVIGATE X4 Study Protocol
90874504 Version AB
Page 38 of 101

*Note: the configuration used for sensed amplitude and lead impedance measurements is upon physician discretion. The nominal sensing configuration for ACUITY X4 is E1 →E2 (LV Tip 1 →LV Ring 2).

The pacing configurations that require PCT testing at the implant (through three-month follow up) are listed in Table 9 below and shown in Figure 8. If the investigator chooses to conduct multiple pacing threshold tests or on configurations not listed below on the ACUITY X4 Lead, only the final measurement and none of the initial measurements taken at 0.5 ms pulse width must be indicated on the eCRF.

Table 9: ACUITY X4 Pacing Configuration Required for PCT Testing at Implant, Pre-D and Three Months Post Implant

Pacing Configurations	# of Configurations tested
Unipolar or extended bipolar measurements from each electrode, E1 through E4	4
Bipolar between electrodes ^Δ : E1 →E2 E1 →E3 E1 →E4	3
Bipolar from the best electrode* on the lead to another electrode on the lead (excluding E1)	1
Total configurations tested	8

* Best electrode is the one that has the lowest threshold without phrenic nerve stimulation (PNS). In the event of a “tie” for best electrode, the investigator should use their medical judgment to select the best.

^Δ Nomenclature of electrodes on the lead (E1, E2, E3, E4) is an industry standard. The corresponding nomenclature on the BSC PRM is as follows:

- E1: LV Tip 1
- E2: LV Ring 2
- E3: LV Ring 3
- E4: LV Ring 4

Figure 8 below depicts the measurements required for the ACUITY X4 leads as described in the table above.

[figure not shown]

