10.7.1.1. PNS Testing

Test for PNS in all aforementioned configurations and measure the PNS threshold if detected in the programmed configuration. The PNS threshold must be documented on the Three-Month technical source documentation form and must be recorded on the Three-Month eCRF.

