11.3.2. Analysis Sets

The following analysis sets will be used for each endpoint. Note that for all analyses, the final lead implanted or attempted from the initial procedure will contribute to the analysis.

Endpoint	Analysis Sets
ACUITY X4 Primary Safety Endpoint	All subjects implanted or attempted with ACUITY X4
ACUITY X4 Primary Effectiveness Endpoint 1	All ACUITY X4 leads with measurements taken at the three-month follow-up visit

December 17, 2013
FINAL

Boston Scientific
NAVIGATE X4 Study Protocol
90874504 Version AB
Page 62 of 101

Endpoint	Analysis Sets
ACUITY X4 Primary Effectiveness Endpoint 1	All ACUITY X4 [REDACTED] leads with measurements taken at the three-month follow-up visit
ACUITY X4 Secondary Effectiveness Endpoints 1 & 2	All ACUITY X4 leads with measurements taken at the three-month follow-up visit
ACUITY X4 Ancillary Safety Objective	Analysis will not be performed at the time of report submission since 60-month data from this study will be pooled with data from an ACUITY X4 Post-Market Approval Study
RELIANCE 4-FRONT Primary Safety Endpoint 1	All subjects implanted or attempted with RELIANCE 4-FRONT
RELIANCE 4-FRONT Primary Safety Endpoint 2	All subjects implanted with RELIANCE 4-FRONT that have been followed for at least [REDACTED] days post-implant
RELIANCE 4-FRONT Secondary Safety Endpoint	All subjects implanted with RELIANCE 4-FRONT that undergo an induction test within 30 days of implant will contribute to the analysis of this endpoint
RELIANCE 4-FRONT Ancillary Safety Objective	Analysis will not be performed at the time of report submission since 60-month data from this study will be pooled with data from a RELIANCE 4-FRONT Post-Market Approval Study
RELIANCE 4-FRONT Primary Effectiveness Endpoint	All RELIANCE 4-FRONT leads with measurements taken at three month follow-up visit
RELIANCE 4-FRONT Secondary Effectiveness Endpoints 1 & 2	All RELIANCE 4-FRONT leads with measurements taken at three month follow-up visit
RELIANCE 4-FRONT Secondary Effectiveness Endpoint 3:	All subjects implanted with RELIANCE 4-FRONT that undergo an induction test within 30 days of implant will contribute to the analysis of this endpoint

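### ACUITY X4 Primary Effectiveness Endpoint 2 has no visible rule for a tested spiral lead with phrenic nerve stimulation on E2, E3 and E4; read literally, such a lead is missing, not a failure

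*Protocol*

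**What the plan says.** Protocol Section 11.1.5 builds Endpoint 2 on the best proximal electrode among E2, E3 and E4, which "will be defined as the electrode with the lowest PCT without PNS". A responder has a PCT of 2.5 V or less there at 3 months, and the goal is a responder rate above 75% (Section 11.1.5.1). Under Section 11.3.1 every primary endpoint for the lead must pass.

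Section 11.1.5.3 makes eligible the "subjects who are successfully implanted with an ACUITY X4 spiral lead", and only those with a best-proximal value contribute. Subjects who do "not have a best proximal zone LV pacing threshold measurement collected at the three month follow-up visit will be considered to have missing data". For them: "The tipping point analysis will consider a range of possible responder rates that could have been observed in the subjects with missing data". No visible text ties a pass or fail to that analysis.

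The analysis-set table in Section 11.3.2 takes "leads with measurements taken at the three-month follow-up visit". Its second row labelled Endpoint 1 is, by position, the row for Endpoint 2.

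At 3 months Table 9 requires "Unipolar or extended bipolar measurements from each electrode, E1 through E4". Section 10.7.1.1 adds: "Test for PNS in all aforementioned configurations and measure the PNS threshold if detected in the programmed configuration". Table 9 and Table 23 say what to do when electrodes tie for best. Neither says what to do when none qualifies. SAP Section 1 defers to the protocol, and SAP Section 2 does not address the point.

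**The concern.** A lead with PNS on all three proximal electrodes has been fully tested. Its thresholds and PNS results are known, and it did not deliver a usable proximal site. That is the outcome the endpoint is there to detect, because Section 11.1.5 explains that the electrodes are clustered on the spiral so that at least one lies against myocardium. Dropping the lead conditions the denominator on part of the success definition and raises the observed rate.

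No other primary endpoint reliably catches it. Paced from E1, the same subject can be a responder on Endpoint 1, which uses the programmed configuration. PNS corrected by reprogramming is an observation in Table 20 and so stays out of the safety endpoint. It counts there only if it meets the complication definition in Section 19.3.1, for example through lead revision.

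**Working it through.** **Plan's own figure.** The synopsis states at least 80% power for all endpoints. The Endpoint 2 assumptions, test and alpha are blacked out, so this cannot be reproduced. What follows is illustrative.

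**Inputs.**
- Goal p0 = 75% (Section 11.1.5.1).
- N = 534 spiral leads (SAP Section 2.1), all assumed tested.
- Exact one-sided binomial test (assumed), at 2.5% and 5%.
- g = share of leads with PNS on all three proximal electrodes. The documents do not give it, so 0 to 5% is shown. Their only figure is PNS in about 30% of CRT patients (Section 3), and g is a subset of such patients.

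**Step 1: critical counts.** The smallest r with P(X ≥ r | n, 0.75) ≤ alpha:
- n = 534: 421 at 2.5%, 418 at 5%.
- n = 519: 409 at 2.5%, 406 at 5%.

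**Step 2: an example near the goal.** Take 410 responders, 109 non-responders and 15 leads with PNS on all three (410 + 109 + 15 = 534).
- As non-responders: 410/534 = 76.8%, P(X ≥ 410 | 534, 0.75) = 0.185. Fails at both levels.
- As missing: 410/519 = 79.0%, P(X ≥ 410 | 519, 0.75) = 0.019. Passes at both levels.

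**Step 3: false-pass chance.** Set the true rate, with these leads counted as failures, at exactly 75%. Draw M ~ Bin(534, g) excluded leads, then X ~ Bin(534 − M, 0.75/(1 − g)) responders. Pass if X reaches the critical count for 534 − M, and sum over M.

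| g | Rate among leads kept | Excluded, 2.5% | Excluded, 5% |
|---|---|---|---|
| 0% | 75.0% | 0.021 | 0.043 |
| 1% | 75.8% | 0.054 | 0.097 |
| 2% | 76.5% | 0.115 | 0.188 |
| 3% | 77.3% | 0.216 | 0.320 |
| 5% | 78.9% | 0.534 | 0.658 |

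Counted as non-responders, the chance stays at 0.021 and 0.043 at every g.

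**Step 4: when it does not matter.** If 90% of the other leads respond and g is 5%, the rate with these leads as failures is 0.90 × 0.95 = 85.5%. The endpoint then passes with probability 1.000 to three decimals under either coding.

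**Step 5: the tipping-point analysis in the Step 2 example.** It asks how many of the 15 would have to respond for the result to hold at n = 534.
- At 5%: 418 − 410 = 8 of 15.
- At 2.5%: 421 − 410 = 11 of 15.
- Expected at the observed rate: 15 × 0.790 = 11.8.

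At 5% the pass looks robust. At 2.5% it looks fragile: with 15 subjects at 79%, the chance of 10 or fewer responders is about 0.19.

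**The case against.** The strongest reply is that the text is unclear and does not actually remove failures. Section 11.1.5.3 speaks of a measurement being collected, which can be read as covering only subjects who were not tested, and this subject's proximal thresholds were collected. The table in Section 11.3.2 keeps leads that have measurements. The responder definition in Section 11.1.5 is positive, so a tested subject who does not meet it could simply be a non-responder. A reader might infer that the protocol contains a rule that discards failed leads. The documents do not support that: exclusion is the most literal of several readings. The objection stands this far. It also shows that analysts could code the same lead differently, and no visible sentence settles it.

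A reader might also infer that the tipping-point analysis would hide the problem. That holds only at 5%. The only alpha visible for ACUITY X4 endpoints is one-sided 2.5%, for the secondary endpoints (Sections 11.1.6.3 and 11.1.7.3), and at that level the example would be flagged as fragile. The range of rates considered could also reach zero. What remains is that the analysis treats a known outcome as unknown and has no visible consequence.

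The size is assumed. Implant testing of each electrode for PNS and the chance to reposition the lead push g down. The 30% figure is PNS of any kind in CRT patients and is not an estimate of g. The example was chosen to sit near the goal. Finally, lines around the Endpoint 2 sample size and analysis are blacked out and could hold a rule, although the visible missing-data sentence carries no exception.

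**Conclusion.** The gap is real: a must-pass endpoint has no visible coding for a lead that was tested and has no PNS-free proximal electrode. The most literal reading drops it as missing although its outcome is a known failure. With a true rate at the goal and 534 leads tested, a 2% share would raise the false-pass chance from 0.021 to 0.115 at one-sided 2.5%, or from 0.043 to 0.188 at 5%. This rests on an assumed share, alpha and test. If the share is near zero, or the response rate is well above 75%, the coding changes nothing. It would be too strong to conclude that the endpoint's error rate is inflated in this trial, because neither the share nor the blacked-out text is known. The clarification should be made; confidence is medium.

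**What to change.** Add to Sections 11.1.5 and 11.1.5.3: *A subject tested at 3 months in whom none of E2, E3 and E4 captures at 2.5 V or less without PNS is a non-responder; missing means not tested.* Limit the Endpoint 2 tipping-point analysis to subjects not tested. Correct the Endpoint 2 row of Section 11.3.2 to match. Report how many subjects had no PNS-free proximal electrode.

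The cost is wording, plus one yes/no PNS field per proximal electrode on the 3-month form if it is not already there. The testing itself is already required. Subjects already tested without a PNS result by electrode would stay unclassified.

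Power falls somewhat. It is P(X ≥ r | 534, R(1 − g)), where R is the response rate among the other leads. With R = 85% and g = 2% the rate is 0.85 × 0.98 = 83.3%, and power is 0.997 at 2.5% (r = 421) or 0.999 at 5% (r = 418). With R = 82% and g = 5% it drops to 0.441 at 5%, but there the true rate is only 0.82 × 0.95 = 77.9%, so the loss is an honest one.

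A separate, secondary suggestion is to fix a standard output for PNS testing. Section 10.7.1.1 states none at 3 months, and at implant analyzer testing (Section 10.5.7) PNS is checked "by pacing the lead at a high voltage output, using professional medical judgment to select the output voltage", so who counts as PNS-free could vary by site.

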11.3.1. Study Success Criteria

The study success will be determined █ for ACUITY X4 and RELIANCE 4-FRONT. Each study will be considered successful if all primary endpoints specific to that lead are passed

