19.3. Definition for Lead-related Adverse Events

Those adverse events deemed related to one of the investigational leads, ACUITY X4 or RELIANCE 4-FRONT, the following definitions will also be applied. Lead-related adverse events include, but are not limited to the following, based on the Advanced Industry Guidance for Uniform Reporting of Clinical Performance of Cardiac Rhythm Management of Pulse Generators and Leads^[37] and FDA Guidance Document^[38]:

- Cardiac perforation requiring surgical intervention
- Cardiac perforation not requiring surgical intervention
- Conductor fracture/ helix damage
- Lead dislodgment
- Failure to capture
- Oversensing
- Failure to sense (undersensing)
- Insulation breach
- Abnormal pacing impedance
- Extracardiac stimulation

December 17, 2013
FINAL

Boston Scientific
NAVIGATE X4 Study Protocol
90874504 Version AB
Page 80 of 101

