2.3 Index Procedure

As stated in the protocol, the final lead implanted or attempted in a chamber from the initial procedure will contribute to the analysis of all applicable endpoints. This criterion will apply separately for ACUITY X4 and RELIANCE 4-FRONT.

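### In the readable text, an index ACUITY X4 lead removed, replaced or disconnected before 3 months for capture failure, elevated threshold or dislodgement is missing, not a non-responder, in both primary effectiveness tests

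*Protocol*

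**What the plan says.** **Eligible and analysed subjects.** Protocol Sections 11.1.4.3 and 11.1.5.3 make successfully implanted subjects eligible (spiral leads for Endpoint 2), but only those with a 3-month threshold contribute data. For Endpoint 1, subjects with no programmed-configuration threshold at "the three month follow-up visit will be considered to have missing data". For Endpoint 2, the same holds for subjects lacking a "best proximal zone LV pacing threshold measurement collected at the three month follow-up visit will be considered to have missing data". No readable sentence distinguishes reasons for absence.

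**Analysis sets.** Section 11.3.2 gives the Endpoint 1 set as "All ACUITY X4 leads with measurements taken at the three-month follow-up visit". A second row, again labelled Endpoint 1 but apparently meant for Endpoint 2, sets the same condition with a redaction.

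**Index lead.** Section 11.3.2 says that "the final lead implanted or attempted from the initial procedure will contribute to the analysis", and SAP Section 2.3 repeats it: "the final lead implanted or attempted in a chamber from the initial procedure will contribute to the analysis of all applicable endpoints".

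**Sensitivity analysis.** Section 11.1.5.3: "The tipping point analysis will consider a range of possible responder rates that could have been observed in the subjects with missing data". Section 11.1.4.3 plans the same.

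**Success.** Section 11.3.1: "Each study will be considered successful if all primary endpoints specific to that lead are passed". Both effectiveness hypotheses use a 75% goal (Sections 11.1.4.1 and 11.1.5.1).

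**The concern.** A lead taken out of service because it would not capture, needed too high an output or had moved out of position is not an unknown outcome. It has failed at what the endpoint measures. Under the readable rules it has no qualifying 3-month value, its replacement may not stand in for it, and it is coded like a missed appointment.

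The error has one direction. If R leads respond among N implanted and k are lost in this way, the test uses R/(N − k) instead of R/N, which is always at least as large. Because every primary endpoint must pass, a responder rate that leaves out known failures could decide the ACUITY X4 verdict when the true rate is close to 75%. At higher rates it still overstates the figure that will be reported.

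The tipping-point analysis shows sensitivity to missing data, but it treats known failures and missed visits as one group. No readable rule links its result to the conclusion.

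**Working it through.** **Plan's own figure.** The synopsis states power of at least 80% for all endpoints. It cannot be reproduced: the sample-size text for these endpoints is redacted (Sections 11.1.4.2 and 11.1.5.2) and no alpha for them is readable. What follows is an illustration of size, not a correction of a stated figure.

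**Inputs from the documents.** Goal 75%. Spiral cohort of 534 (SAP Section 2.1, which counts enrolments, so the implanted number may differ).

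**Assumptions.** Exact one-sided binomial test; alpha 2.5%, with 5% as an alternative; share f of index leads lost to capture failure, elevated threshold or dislodgement of 1% to 5%.

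**Step 1: pass probability when the true all-implanted rate p is exactly 75%.** k = round(N × f), n = N − k. The responder rate among measured leads is p × N/n. The critical value c is the smallest count with P(X ≥ c | n, 0.75) ≤ alpha. Then P(X ≥ c) is taken at the measured-lead rate.

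| f | k | Pass mark, alpha 2.5% | Pass mark as share of 534 | P(pass), alpha 2.5% | P(pass), alpha 5% |
|---|---|---|---|---|---|
| 0 | 0 | 421/534 | 78.8% | 2.1% | 4.3% |
| 1% | 5 | 417/529 | 78.1% | 5.1% | 9.3% |
| 2% | 11 | 412/523 | 77.2% | 12.7% | 20.5% |
| 3% | 16 | 409/518 | 76.6% | 20.1% | 30.2% |
| 5% | 27 | 400/507 | 74.9% | 54.8% | 67.2% |

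In the last row the test can pass with responders making up less than 75% of implanted leads. With N = 480 and alpha 2.5%, the pass probability goes from 2.4% to 5.9%, 10.4%, 17.4% and 48.2%.

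**Step 2: higher true rates (N = 534, alpha 2.5%, f = 1%).** Measured-only against losses counted as non-responders: 88.0% against 76.7% at a true 80%; 99.2% against 97.3% at 82%; both above 99.9% at 85%. Here a pass is the correct verdict, so the effect on it fades.

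**Step 3: overstatement of the reported rate at a true 85%.** f = 1%: 0.85 × 534/529 = 0.858, or 0.8 points too high. f = 3%: 0.85 × 534/518 = 0.876, or 2.6 points too high.

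**Step 4: effect of pooling (assumed counts).** Take 534 implanted, 11 lost to the three causes, 27 missing for other reasons, and 395 responders among 534 − 38 = 496 measured.

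- Observed rate: 395/496 = 79.6%. The pass mark is 392, so the planned test passes.
- Pooled tipping point: 421 − 395 = 26 responders needed among 38 missing, or 68%. That is below the observed rate, so the result looks robust.
- With the 11 counted as non-responders: 395 of 496 + 11 = 507, pass mark 400. The test does not pass.
- With only the 27 treated as missing: 26 of 27, or 96%, would have to be responders.

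**The case against.** **Redaction.** Blacked-out lines stand between the contribution sentence and the missing-data sentence in both sections, so a handling rule may exist. This stands. The point is confined to readable text; Section 11.3.2 has no such rule in its readable text.

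**Switched-off leads.** A reader might infer that any lead out of use at 3 months is missing. The documents do not support that. Section 10.7.1 requires threshold testing of all implanted ACUITY X4 leads in the Table 9 configurations, so a connected lead that is merely switched off must still be tested. It need not be missing, at least for Endpoint 2, which uses the best proximal electrode rather than the programmed configuration.

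**All lead-related losses.** A reader might also infer that every lead-related loss is a hidden non-response. The endpoint is a threshold. A lead lost to perforation, insulation breach, extracardiac stimulation or "Conductor fracture/ helix damage" (Section 19.3) may have had a low one. Counting all of these as non-responders in the primary analysis would be a choice of estimand, not the correction of an error. This stands and limits the claim to three causes.

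**Safety endpoint.** Lead-related losses generally count as complications in the primary safety endpoint (Section 11.1.1), which must also pass. So the plan does not ignore these failures. But that endpoint has its own goals (87% and 85%, Section 11.1.1.1) and does not correct the rate tested against 75%.

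**Tipping point.** Nothing readable excludes a 0% responder rate, so the worst case may be covered, and dislodgement rates are summarised separately (Section 11.1.8.2). A careful reader of the example could see that at most 27 of 38 (71%) could respond, against a tipping point of 68%. That is fair, but the reader would have to reconstruct it, and the primary test stays as it is.

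**Conclusion.** The point holds in a limited form. In the readable text, index leads explanted, replaced or disconnected before 3 months for failure to capture, elevated threshold or dislodgement drop out of both primary effectiveness tests as missing. This can only raise the responder rate, and the planned sensitivity analysis does not separate them from missed visits.

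The documents do not support the inference that the trial is likely to pass wrongly. The number affected is unknown and probably small. The verdict is at risk mainly when the true rate is near 75%. The illustrated rise from 2.1% to 5% (1% lost) or 20% (3% lost) rests on an assumed N, alpha, test and loss share. By a true 85% only the reported rate is affected. A wording change is worthwhile; confidence is medium because of the redactions.

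**What to change.** In Sections 11.1.4.3, 11.1.5.3 and 11.3.2, state that:

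- an implanted index ACUITY X4 lead with no 3-month threshold because it was explanted, replaced or disconnected for failure to capture, elevated threshold or dislodgement counts as a non-responder in the primary analysis;
- a repositioned index lead with a valid 3-month measurement keeps its observed value;
- leads lost to other lead-related events (for example perforation, insulation breach, conductor fracture or extracardiac stimulation) are counted as non-responders in a pre-specified sensitivity analysis;
- missing thresholds are reported by reason, and the tipping-point analysis covers the remaining missing subjects and includes the scenario in which all are non-responders.

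If a redacted line already sets such a rule, align Section 11.3.2 with it. Section 9.3, which puts implanted subjects in all effectiveness analyses, should also be squared with the measured-only sets.

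The cost is protocol and SAP wording, and a slightly less favourable responder rate.
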